1. PROTOCOL SYNOPSIS

This Phase 3 study will evaluate the efficacy and safety of daprodustat (GSK1278863) compared to recombinant human erythropoietin (rhEPO) in the treatment of anemia associated with chronic kidney disease (CKD) in subjects who are planning to start or who have recently started dialysis. This study will also provide information on daprodustat dosing initiation and titration in subjects initiating dialysis.

Primary Objective/Primary Efficacy Endpoint

The primary objective of the study is to compare daprodustat to rhEPO for hemoglobin (Hgb) efficacy (non-inferiority).

The primary efficacy endpoint will be the mean change in Hgb between baseline and the evaluation period (EP, mean over Weeks 28-52).

Overall Design

- This is a randomized, open-label (sponsor blind), active-controlled, parallel-group, multi-center study in subjects with anemia associated with CKD who are not regularly using erythropoiesis-stimulating agents (ESAs) and who are initiating dialysis.
- This study will comprise three study periods: a screening period (2 weeks*), a 52-week active treatment period, and a follow-up period (4-6 weeks).

* Screening period can be extended by an additional 4 weeks for ultrasound examination, IV iron supplementation and/or vitamin B12 treatment as needed.

- Subjects will be stratified by dialysis type (hemodialysis [HD], or peritoneal dialysis [PD]) and by whether their dialysis start is planned or unplanned (urgent).
- Following stratification, subjects will be randomized 1:1 to receive daprodustat or rhEPO (darbepoetin alfa); all randomized treatments (Section 6.1) will be supplied by GSK.
- Although prior regular ESA use is prohibited, limited ESA use is allowed around the time of dialysis initiation only.
- To ensure consistency of treatment across the study there are protocol-mandated algorithms for dose adjustments of daprodustat and rhEPO, iron management, and rescue.

Type and Number of Subjects

- The study will enroll the following types of subjects with anemia associated with CKD: Planned initiation of dialysis: Subjects who are planning to start chronic dialysis (HD or PD) within the next 6 weeks (from the day of screening).

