- **Unplanned (urgent) initiation of dialysis:** For Subjects who have started chronic dialysis in an urgent manner, meaning they started HD with a temporary vascular access with no previous planning for chronic dialysis or have started PD with recent (< 2 weeks) PD catheter insertion and/or who have not been seen by a kidney specialist (nephrologist) or other specialist with expertise in dialysis care within previous 4 months prior to screening.

This study will randomize approximately 300 subjects, or 150 subjects per treatment group.

Primary Efficacy Analysis

The primary Hgb efficacy analysis will assess whether daprodustat is non-inferior to rhEPO for change from baseline. The analysis will be based on the mean change in Hgb between baseline and the efficacy EP (defined as Weeks 28 to 52) using a non-inferiority margin of -0.75 g/dL (two-sided 95% CI). An analysis of the ITT Population, comprising all subjects with at least one Hgb measurement (on or off-treatment) during the EP and an analysis of covariance (ANCOVA) model will be used. The model will include randomization stratification factors, and factors for baseline Hgb and treatment.

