9.4.4.1. Exploratory Cardiovascular Safety Analysis

This study is not designed or sufficiently powered for formal statistical analyses to assess cardiovascular safety. With fewer than 80 first MACE (defined as all-cause mortality, non-fatal MI, or non-fatal stroke) expected to occur during the trial, incidence rates and two-sided 95% CIs will be computed for the following mortality and CV composite or component endpoints: 1) MACE; 2) MACE or a thromboembolic event (vascular access thrombosis, a symptomatic deep vein thrombosis or a symptomatic pulmonary embolism); 3) MACE or hospitalization for heart failure; 4) all cause mortality; 5) CV mortality; 6) MI (fatal and non-fatal); 7) stroke (fatal and non-fatal); 8) CV mortality or non-fatal MI; 9) all cause hospitalization.

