
 For the MMRM analysis of change from baseline in Hgb, the NI margin used in the primary analysis of Hgb (-0.75 g/dL) will be used for reference in this comparison, thus generating support for non-inferiority if the lower bound of the two-sided 95% CI is above -0.75 g/dL. For the responder analysis, the one-sided CMH p-value will be compared to 0.025 to assess nominal significance. For the percent time in range analysis, a NI margin of -15% will be used as a reference in this comparison, thus generating support for non-inferiority if the lower limit of the two-sided 95% CI of Hodges-Lehmann estimate is above -0.15. If non-inferiority is established, nominal superiority will be achieved if the one-sided p-value from the van Elteren test is < 0.025.

Supportive Statistical Analyses
Subgroup Analysis

 Subgroup analyses will be performed for all Hgb variability endpoints, using the stratification factor subgroups only (described in Section 0).

Time to Rescue

Additional Secondary Efficacy Statistical Analyses: Time to Rescue
Endpoint(s)

 Time to stopping randomized treatment due to meeting rescue criteria
Model Specification

 The Cox Proportional Hazards model will adjust for the following baseline categorical values: 
 Treatment Dialysis type (as randomized, see Section 0) Dialysis start manner (whether dialysis start is planned or unplanned; as randomized, see Section 0)

CONFIDENTIAL

201410

Additional Secondary Efficacy Statistical Analyses: Time to Rescue

 Confidence intervals for the rate per 100 person-years will also be reported. For within-group rates, the 95% CI will be obtained using an exact Poisson method. For difference in rates between treatments, the two-sided 95% CI will be constructed with a Normal approximation using Wald's method [Liu, 2006]. Analysis will include only those efficacy endpoints occurring within the time period for treatment discontinuation. Calculation of time-to-event or censoring is described in further detail in Section 10.6.3. Time to stopping study medication due to meeting rescue criteria is defined as the time from Randomization until the date on which a subject permanently stops study medication due to meeting criteria for rescue.
Model Results Presentation

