8.2.2.4. Planned Exploratory Cardiovascular Safety Analysis Details

Exploratory CV Safety Analyses
Endpoint(s)¹:

 • MACE (all-cause mortality, non-fatal MI, or non-fatal stroke) • MACE or a thromboembolic event • MACE or hospitalization for HF • All-cause mortality • CV mortality • MI (fatal and non-fatal) • Stroke (fatal and non-fatal) • CV mortality or non-fatal MI • All-cause hospitalization
Model Specification

 • For all exploratory CV endpoints, confidence intervals for the rate per 100 person-years will be reported. For within-group rates, the 95% CI will be obtained using an exact Poisson method. For difference in rates between treatments, the two-sided 95% CI will be constructed with a normal approximation using Walds' method [Liu, 2006]. • • For MACE endpoint, the calculation of time-to-event or censoring is described in further detail in Section 10.6.4.1. • First occurrence of adjudicated MACE for a subject is defined as the first adjudicated event, determined by the event date, which is indicated as all-cause mortality, non-fatal MI or non-fatal stroke with further details in Section 10.6.4.1. • For those endpoints or components of endpoints intended to go through the adjudication process, only the adjudicated results will be used.
Model Results Presentation

 • A summary of the number and percentage of subjects having first-occurrence MACE will be provided by treatment group. The number and percentage of the types of events that make up the first occurrence of MACE will also be provided by treatment group. This summary table will be repeated for MACE plus thromboembolic events, for MACE plus hospitalization for heart failure and for MACE plus thromboembolic events or hospitalization for CHF.

CONFIDENTIAL

201410

Exploratory CV Safety Analyses

- A summary of all MACE including the number and percentage of subjects and number of events (including first and subsequent MACE) by type of event will be provided by treatment group.
- A summary of the number and percentage of subjects having first-occurrence adjudicated COVID-19 MACE will be provided by treatment group. The number and percentage of the types of events that make up the first occurrence of adjudicated COVID-19 MACE will also be provided by treatment group.
- Summaries of adjudication details of all-cause mortality will include the number and percentage of subjects by cause of death.

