- Summaries of adjudication details of MI will include the number and percentage of events by outcome of MI (fatal or non-fatal), type of MI, increased cardiac markers (y/n), ST segment classification [ST-elevation myocardial infarction (STEMI), non-ST-elevation myocardial infarction (NSTEMI), ECG not interpretable, ECG not available], and Q wave classification (Q wave MI, Non Q wave MI, ECG not interpretable, ECG not available).
- Summaries of adjudication details of stroke will include the number and percentage of events by outcome of stroke (fatal or non-fatal), type of stroke (ischemic, hemorrhagic, or undetermined) and ischemic details (with/without hemorrhagic transformation) and location if hemorrhagic (intraparenchymal, intraventricular, subarachnoid, retinal, unknown location).
- Summaries of adjudication details of heart failure will include the number of events by type: hospitalization for heart failure, heart failure requiring urgent ER/ED visit, heart failure requiring urgent office/practice visit, and fatal heart failure events identified by cause of death only.
- Summaries of adjudication details of thromboembolic events will include the number and percentage of events by type of thromboembolic event (DVT, PE, VAT).
 - Summaries of PEs will include outcome of PE (fatal or non-fatal).
 - Summaries of VATs will include type of VAT (AV fistula, AV graft, central venous catheter, other), method of diagnosis (ultrasound/Doppler, AV imaging, CVC imaging, other), and treatment (thrombolytic therapy, thrombectomy, angioplasty, stent, surgical intervention, not specified).
- A summary of adjudicated exploratory CV endpoints above (except all-cause hospitalization) will be provided to include the number and percentage of subjects and the number of events for each endpoint.
- The model results presentation for the endpoints above (except all –cause hospitalization) will be provided to include within-group incidence rates per 100 person-years (along with two-sided 95% CI), and difference in rates between treatments (along with two-sided 95% CI), For composite endpoints, the number and percentage of the type of first occurrence will be provided by treatment group.
- A summary of all-cause hospitalization will be provided by treatment group including summaries of the number of hospitalizations per subject, average length of stay per hospitalization and primary diagnosis at discharge by system organ class and lower level term.

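### The Wald interval for the between-arm difference in CV event rates has no sparse-count rule: it is degenerate at 0 vs 0 events and falls short of 95% coverage when events are few and the true rates differ

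*SAP*

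**What the plan says.** The model specification in SAP 8.2.2.4 covers all nine exploratory CV endpoints: MACE, two wider composites, all-cause and CV mortality, MI, stroke, CV mortality or non-fatal MI, and all-cause hospitalization. Within arms: "For within-group rates, the 95% CI will be obtained using an exact Poisson method". Between arms: "For difference in rates between treatments, the two-sided 95% CI will be constructed with a normal approximation using Walds' method". The results presentation in the same section asks for the "difference in rates between treatments (along with two-sided 95% CI") for each endpoint except all-cause hospitalization. Nothing is said about what to do when one or both arms have few or no events.

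Protocol 9.4.4.1 sets the status of the analysis: "This study is not designed or sufficiently powered for formal statistical analyses to assess cardiovascular safety". It also gives the only CV event forecast: "With fewer than 80 first MACE (defined as all-cause mortality, non-fatal MI, or non-fatal stroke) expected to occur during the trial". That is a ceiling on a composite; no number is given for stroke, MI or CV death separately. On size, the protocol synopsis states: "This study will randomize approximately 300 subjects, or 150 subjects per treatment group", with a 52-week treatment period and 4-6 weeks of follow-up.

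The same method appears for time to rescue in SAP 8.1.2.2: "For difference in rates between treatments, the two-sided 95% CI will be constructed with a Normal approximation using Wald's method".

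**The concern.** The plan uses an exact method where each arm stands alone and a large-sample approximation for the contrast. The Wald variance is built from the observed counts, so an arm with no events contributes no variance. An endpoint with no events in either arm would print a zero-width 95% interval next to two within-arm intervals that each allow a rate well above zero.

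Short of that extreme, the interval can be too narrow for rare components. A reader looks at the limit on the side of an excess to judge how large a difference remains compatible with the data. If that limit stops short too often, the 95% label is wrong on the figure that matters most. With no pre-specified rule, a degenerate interval would also have to be handled by an ad hoc choice after unblinding.

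**Working it through.** **Inputs.** From the documents: 150 subjects per arm, 1:1 allocation, about one year of follow-up, fewer than 80 first MACE in total. Assumed: 140 PY per arm (range 120-160, allowing for losses and for the follow-up visit), Poisson counts, and a range of true component rates, since none are given.

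**Formulas.** The SAP does not print the Wald formula; the usual form is used. With counts x and y and T person-years in each arm:

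- Wald: (x − y)/T ± 1.96 × √(x + y)/T.
- Score: all differences δ with |(x − y)/T − δ| ≤ 1.96 × √((r₁ + r₂)/T), where r₁ and r₂ are the maximum-likelihood rates constrained to differ by δ.

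Coverage is the summed Poisson probability of all (x, y) whose interval contains the true difference.

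**The plan's own 95% at MACE scale.** Fewer than 80 first MACE means up to 80/2 = 40 per arm if rates are equal. For 40-80 expected events in total and rate ratios from 1 to 4, Wald coverage is 94.7-95.1%. The nominal level is reproduced there. It is 94.4-95.2% for 20-40 events and 93.4-95.7% for 10-20.

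**Individual datasets** (140 PY per arm, daprodustat minus darbepoetin, per 100 PY):

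| Events | Wald | Score |
|---|---|---|
| 0 vs 0 | 0.00 to 0.00 | −2.74 to 2.74 |
| 1 vs 0 | −0.69 to 2.11 | −2.03 to 4.05 |
| 0 vs 2 | −3.41 to 0.55 | −5.21 to 1.32 |
| 4 vs 0 | 0.06 to 5.66 | 0.11 to 7.35 |

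At 0 vs 0 the exact within-arm upper limit is 3.689/140 = 2.63 per 100 PY. The score limit there solves √(140δ) = 1.96, so δ = 3.84/140 = 2.74 per 100 PY.

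**Coverage with unequal rates** (140 PY per arm; expected total = sum of the two rates × 1.4):

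| Rates per 100 PY | Expected total | Wald | Score | Wald upper limit below true excess |
|---|---|---|---|---|
| 1.0 vs 0.25 | 1.75 | 75% | 99% | 24.7% |
| 1.0 vs 0.5 | 2.1 | 87% | 99% | 13.1% |
| 1.5 vs 0.5 | 2.8 | 87% | 98% | 12.4% |
| 3.0 vs 0.5 | 4.9 | 91% | 96% | 8.3% |
| 2.0 vs 1.0 | 4.2 | 92% | 97% | 7.0% |
| 3.0 vs 2.0 | 7.0 | 95% | 95% | 3.8% |

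The nominal value for the last column is 2.5%. Swapping the arms mirrors the result: at 0.25 vs 1.0, 24.7% of intervals lie entirely above the true (negative) difference. Across 120-160 PY, Wald coverage in the first five rows is 75-94%. The score interval is at or above 94% except at 3.0 vs 0.5 with 160 PY, where it is 93%.

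**How much is the 0-0 outcome.** At 1.0 vs 0.5 its probability is exp(−2.1) = 12.2%, which is most of the 13.1%. At 3.0 vs 0.5 it is exp(−4.9) = 0.7%, against misses of 8.3%, so the shortfall is not confined to empty endpoints.

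**Coverage with equal rates** (140 PY): 99.4% at 0.5 vs 0.5, 97.3% at 1 vs 1, 95.3% at 2 vs 2, 95.6% at 3 vs 3.

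**Excluding zero.** At δ = 0 the constrained common rate is (x + y)/(2T), so the score variance is (x + y)/T², the same as Wald. With equal person-time the two intervals therefore exclude zero in exactly the same datasets.

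**The case against.** The strongest reply is that little depends on this interval. The protocol disclaims formal CV assessment, no test or margin is attached, and the Wald method is pre-specified with a cited reference. Exact within-arm limits sit beside it, so a reader who sees 0 vs 0 is not left with [0, 0] alone. The sparse scenarios are assumed, because the documents forecast only MACE. All of this stands, and it sets the priority.

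Four stronger readings are tempting, and the documents do not support them.

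- A reader might infer that the interval collapses whenever one arm is empty. It does not: 1 vs 0 gives −0.69 to 2.11. Zero width needs both arms empty.
- A reader might infer poor coverage at this trial's event counts in general. The only count given is for MACE, where coverage is about 95%; how sparse the components will be is unknown.
- A reader might infer that the method hides harm signals. With equal person-time it excludes zero exactly when the score interval does. What it understates is the possible size of a difference, in either direction.
- A reader might take this as the only between-arm CV inference. SAP 8.2.3.2 plans relative-risk intervals for the adverse events of special interest, which include a composite of death, MI, stroke, heart failure and thromboembolic events, and SAP 8.2.2.4 adds a comparative Kaplan-Meier plot for MACE.

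For rescue, no shortfall has been shown. SAP 8.1.2.2 already reports a Cox hazard ratio with an interval, and its results presentation does not list the rate-difference interval.

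**Conclusion.** The point holds in a limited form. For endpoints with about 5 or fewer expected events in total and unequal true rates, an interval labelled 95% covers about 75-92% at an assumed 140 PY per arm, mostly because the limit on the side of the excess does not reach the true difference. For an endpoint with no events it has no width at all. With equal rates, or about 10 or more events, the method performs close to its label or conservatively.

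The size rests on assumed component rates, Poisson counts and equal person-time. The zero-width result at 0 vs 0 needs none of these. Because the analysis is exploratory and decides nothing, this is a low-priority correction.

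**What to change.** In SAP 8.2.2.4, replace the Wald interval for the difference in incidence rates with a score interval (Miettinen-Nurminen type) for a difference of two Poisson rates, and keep the exact Poisson intervals within arms. The score interval has positive width at 0 vs 0 and approaches the Wald interval as events accumulate, so one rule can serve every endpoint in the section.

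The matching sentence for rescue in SAP 8.1.2.2 may be aligned for consistency, but it matters less.

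The cost is one sentence of SAP text and a small programming change before unblinding, and wider intervals for the sparse endpoints.

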8.2.3. Adverse Event Safety Analyses

Adverse events will be coded using the Medical Dictionary for Regulatory Activities (MedDRA) coding dictionary. For the purpose of AE summaries and analysis, the investigator-reported AE details will be used, regardless of the adjudication outcome of the event.

See Section 10.4.1 for AE treatment state definitions. The adverse event safety analyses will be based on the Safety population, unless otherwise specified.

8.2.3.1. Overview of Planned Adverse Event Analyses

Table 11 provides an overview of the planned adverse event safety analyses.

Table 11 Overview of Planned Adverse Event Safety Analyses

Parameter	Absolute			
	Summary		Individual	
	T	F	F	L
AESIs				
Summary of AESIs	Y	Y		
Adverse Events				
All AEs by System Organ Class (SOC) and Preferred Term	Y			Y
All AEs by System Organ Class (SOC) and Preferred Term (subjects and occurrences)	Y			
All AEs by SOC and Preferred Term by Subgroups	Y			
All AEs by Overall Frequency	Y			
Common AEs by Overall Frequency	Y	Y ¹		
All AEs by Maximum Intensity	Y			
All Drug-Related AEs by Maximum Intensity	Y			
All Drug-Related AEs by SOC and Preferred Term	Y			
Common Non-Serious AEs by SOC and Preferred Term (subjects and occurrences)	Y			
Subject Numbers for Individual AEs				Y
Relationship Between AE SOCs, Preferred Term & Verbatim Text				Y
Pregnancy Data				Y
Serious and Other Significant Adverse Events				
SAEs by SOC and Preferred Term (subjects and occurrences)	Y			
SAEs by Maximum Intensity	Y			
Reasons for Considering as a SAE				Y

CONFIDENTIAL

201410

Parameter	Absolute			
	Summary		Individual	
	T	F	F	L
Drug-Related SAEs by SOC and Preferred Term (subjects and occurrences)	Y			
Fatal SAEs by SOC and Preferred Term (subjects and occurrences)	Y			Y
Non-Fatal SAEs by SOC and Preferred Term (subjects and occurrences)	Y			Y
Drug-Related Fatal SAEs by SOC and Preferred Term (subjects and occurrences)	Y			
AEs Leading to Permanent Discontinuation of Randomized Treatment by SOC and Preferred Term	Y			Y
BP Exacerbation Events	Y			
BP Exacerbation SAEs	Y			
Other Significant AEs				Y

NOTES :

- T = Table, F = Figure, L = Listing, Y = Yes display generated.
- Summary = Represents TFL related to any summaries (i.e. descriptive statistics) of the observed raw data.
- Individual = Represents FL related to any displays of individual subject observed raw data.

[1]: Plot of common AEs and relative risk will be generated.

8.2.3.2. Planned Adverse Event Safety Statistical Analyses*AESIs Analyses*

Adverse events of special interest are described in Section [10.6.4](#).

Summaries of AESIs will include the number, percentage and rate per 100 person-years of subjects having at least one occurrence, the number of events, the number of subjects by number of occurrence, the characteristics of the AE (serious, drug-related, etc.), outcome, maximum intensity, time to first onset/worsening, and action taken summarized by treatment group. For each count, a subject will be summarized as follows:

- Serious/drug-related/severe/fatal: If any specific AE falls in the respective category, the subject will be counted in that category.
- Outcome: The subject will be counted within a category if there is at least one specific AE in that category.
- Maximum intensity: The specific AE with the maximum intensity will be counted for this purpose. For example, a subject will be counted in the 'severe' category if there is at least one specific AE with severe intensity. A subject will be counted in the 'moderate' category if there is at least one specific AE with moderate intensity and there is no specific AE with severe intensity.
- Time to first onset/worsening (days): The earliest of onset dates for the specific AE – treatment start + 1

CONFIDENTIAL

201410

If the AE onset date/AE worsening and/or resolution date is missing or incomplete in the database for any occurrence of the specific AE, time to first onset /worsening will be left missing for the subject. These summaries of special interest AEs will be provided for those AEs classified as treatment emergent.

Cumulative incidence function (CIF) plots may be produced for each AESI summarizing the time to first occurrence of the AESI by treatment group, with the exception of the composite endpoint AESI (death, myocardial infarction, stroke, heart failure, thromboembolic events, thrombosis of vascular access). This endpoint will use a Kaplan-Meier plot. If there are less than 20 subjects total for both the daprodustat and darbepoetin alfa arm, then these plots will not be created. Competing risks for the AESI cumulative incidence plots include:

AE of Special Interest (Event of interest)	Competing Risk Events
Thrombosis and/or tissue ischemia secondary to excessive erythropoiesis	Death due to any cause prior to the AESI
Cardiomyopathy	Death due to any cause prior to the AESI
Pulmonary artery hypertension	Death due to any cause prior to the AESI
Cancer-related mortality and tumor progression and recurrence	All other non-cancer-related death prior to the AESI (use death date as the competing risk date)
Esophageal and gastric erosions	Death due to any cause prior to the AESI
Proliferative retinopathy, macular edema, choroidal neovascularization	Death due to any cause prior to the AESI
Exacerbation of rheumatoid arthritis	Death due to any cause prior to the AESI
Worsening of hypertension	Death due to any cause prior to the AESI

Dot plots displaying the incidence of the event will be provided for AESIs by AESI term and treatment group. The incidence rate in each treatment group and corresponding two-sided 95% confidence interval for the relative risk of the daprodustat group compared to the darbepoetin alfa group will be provided.

Adverse Events

The number and percentage of subjects reporting at least one AE will be provided for each treatment group. These events will be summarized by treatment group, primary system organ class, and preferred term. Pre-treatment and treatment emergent AEs will be summarized separately.

The number and percentage of subjects and the number of occurrences of all treatment emergent AEs will be summarized by primary system organ class, and preferred term.

Summaries of all treatment emergent AEs will be produced for the age group, gender, race group, baseline dialysis type, baseline dialysis start manner, and weight quartile subgroups. Summaries of treatment emergent AEs by subgroup will be produced twice: by system organ class and preferred term and separately by overall frequency.

A listing of AE records for all subjects who reported AEs will be produced.

Summaries of all treatment emergent AEs will be provided by maximum intensity. For AEs reported more than once by a subject, the most severe intensity will be included in summaries where applicable. The max intensity will be presented as “Unknown” if Missing and/or N/A are the only available severity values. Analysis will be repeated for all drug-related treatment emergent AEs.

The number and percentage of subjects reporting the most common treatment emergent AEs (those occurring in $\geq 5\%$ of subjects in any treatment group) will be summarized by preferred term and treatment group.

Additionally, the most common treatment emergent AEs will be summarized graphically by preferred term and treatment group. The incidence rate in each treatment group and corresponding two-sided 95% confidence interval for the relative risk of the daprodustat group compared to the darbepoetin alfa group will be provided. Displays will be sorted by magnitude of risk, from largest to smallest.

The number and percentage of subjects reporting treatment emergent AEs assessed by the investigator to be related to the study drug will be summarized by treatment group, primary system organ class, and preferred term, and separately by overall frequency

The number and percentage of subjects and the number of occurrences of common non-serious treatment emergent adverse events (those occurring in $\geq 5\%$ of subjects in any treatment group) will be summarized by primary system organ class, preferred term, and treatment group, and separately by overall frequency.

A listing of which subjects reported specific adverse events will be produced.

The hierarchical relationship between MedDRA SOCs, PTs and verbatim text will be listed for all adverse events.

A listing of subjects who became pregnant while participating in the study will be provided.

Serious and Other Significant Adverse Events

The number and percentage of subjects and the number of occurrences of treatment emergent SAEs will be provided for each treatment group. These events will be summarized by treatment group, primary system organ class, and preferred term. Treatment emergent SAE preferred terms will also be summarized by treatment group and overall frequency.

Summaries of treatment emergent SAEs will be provided by maximum intensity.

A listing of reasons for considering as a SAE will be produced for all treatment emergent SAEs.

The number and percentage of subjects and the number of occurrences of treatment emergent drug-related SAEs, fatal SAEs, non-fatal SAEs, and drug-related fatal SAEs will be summarized by treatment group: by primary system organ class and preferred term and separately by overall frequency.

A listing of treatment emergent fatal SAE records and a listing of treatment emergent non-fatal SAE records will be provided.

The number and percentage of subjects reporting treatment emergent AEs leading to discontinuation of randomized treatment will be summarized by treatment group, primary system organ class, and preferred term.

A listing of treatment emergent AEs leading to discontinuation of randomized treatment will be provided.

BP events and BP-related SAEs are defined in Section 10.6.4.

The number and percentage of subjects with at least one on-treatment BP event will be provided for each treatment group. In addition, this summary will include the number and percentage of subjects with at least one on-treatment BP event that is considered clinically significant and the number and percentage of subjects with at least one on-treatment BP event that is considered to be symptomatic.

The number and percentage of subjects reporting at least one treatment emergent BP-related SAE will be provided for each treatment group. In addition, the number of on-treatment BP-related SAEs will be summarized by treatment group, primary system organ class, and preferred term.

A listing of other significant adverse events will be produced. Other significant adverse events are events that are not reported as fatal or serious but represent ICH-defined 'Other significant adverse events' (i.e., marked haematological and other laboratory abnormalities and any adverse events that led to an intervention, including withdrawal of drug treatment, dose reduction, or significant additional concomitant therapy). For this study, other significant AEs will be defined as non-fatal non-serious AEs resulting in an action taken with study treatment of either 'dose interrupted/delayed' or 'dose reduced'.

Other CV Events

GSK has identified other CV events of interest for all clinical studies. In this study, investigators will be required to fill out the specific CV event page of the eCRF for the following CV AEs and SAEs or any event that may potentially be one of the categories listed:

- Arrhythmias
- Pulmonary hypertension
- Valvulopathy

CONFIDENTIAL

201410

- Revascularization

Electronically generated patient profiles for subjects reporting these events will not be prospectively created.

